- Serum bilirubin  $\leq$  1.5  $\times$  institutional upper limit of normal (ULN).
- AST (SGOT)/ALT (SGPT)  $\leq$  2.5  $\times$  institutional ULN
- Creatinine CL $>40$  mL/min by the Cockcroft-Gault formula (Cockcroft and Gault 1976) or by 24-hour urine collection for determination of creatinine clearance:

Males:

$$\text{Creatinine CL} = \frac{\text{Weight (kg)} \times (140 - \text{Age})}{72 \times \text{serum creatinine (mg/dL)}}$$

Females:

$$\text{Creatinine CL} = \frac{\text{Weight (kg)} \times (140 - \text{Age})}{72 \times \text{serum creatinine (mg/dL)}} \times 0.85$$

2.1.1.8 Female subjects must either be of non-reproductive potential (i.e., post-menopausal as described below) OR history of surgical sterilization (hysterectomy, bilateral tubal ligation, or bilateral oophorectomy) or must have a negative serum pregnancy test upon study entry.

- Women <50 years of age would be considered post-menopausal if they have been amenorrheic for 12 months or more following cessation of exogenous hormonal treatments and if they have luteinizing hormone and follicle-stimulating hormone levels in the post-menopausal range for the institution
- Women ≥50 years of age would be considered post-menopausal if they have been amenorrheic for 12 months or more following cessation of all exogenous hormonal treatments, had radiation-induced menopause with last menses >1 year ago, or had chemotherapy-induced menopause with last menses >1 year ago

2.1.1.9 The effects of Vicineum and durvalumab on the developing human fetus are unknown. Females of childbearing potential and men who are sexually active must use a highly effective method of contraception (including abstinence, intrauterine system or intrauterine device contraceptive implant, hormonal, female or partner sterilization or menopause as defined in 2.1.1.8) and a second form of barrier contraception during study treatment and for 120 days after the last dose of study drug. Note: partner's use of the same methods of contraception (barrier, hormonal, intrauterine device [IUD], surgical sterilization) is also acceptable. Should a woman become pregnant or suspect she is pregnant while she or her partner is participating in this study, she should inform her treating physician immediately.

2.1.1.10 Written informed consent obtained from the subject prior to performing any protocol-related procedures

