  - Coagulation parameters (PT, PTT)

- Viral Studies (Hepatitis B and C; HIV)
- Thyroid function tests
- Urinalysis
- 24 hour urine (only if CrCL will not be calculated)
- PPD if indicated
- Computerized Tomography (CT) urogram or Magnetic Resonance Imaging (MRI) urogram. If urogram protocol not available or contrast allergy/poor renal function preclude such imaging, then CT or MRI of the abdomen/pelvis without contrast will suffice and investigator may perform retrograde pyelogram at their discretion.
- Electrocardiogram (ECG) for QT interval – Mean QT interval corrected for heart rate using Fridericia's formula (QTcF) will be calculated from a single ECG. If QTcF  $\geq$  470ms, then the patient must be excluded from trial.
  - Resting 12-lead ECGs will be recorded according to the assessment schedule. ECGs should be obtained after the patient has been in a supine position for 5 minutes and should be recorded while the patient remains in that position.
  - ECG will be recorded at Screening, in Week 2 (pre-durvalumab treatment) and as clinically indicated.
  - In case of clinically significant ECG abnormalities, including a QTcF value  $>470$  ms, 2 additional 12-lead ECGs should be obtained over a brief period (e.g., 30 minutes and at least 5 minutes apart) to confirm prolongation
- Serum or urine beta-HCG for women of child-bearing age

See section **3.4, Study Calendar** for more details.

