##### **3.1.1 Dose Limiting Toxicity (DLT)**

A DLT will be defined as any Grade 3 or higher toxicity that occurs during the initial 6-week period the subject is on treatment (i.e., the DLT evaluation period). Toxicity that is clearly and directly related to the primary disease or to another etiology is excluded from this definition. Since this trial also involves immunotherapy, immune-related AEs (irAEs) are defined as AEs of an immune nature (i.e. inflammatory) in the absence of a clear alternative etiology. In the absence of a clinically significant abnormality, repeat laboratory testing will be conducted to confirm significant laboratory findings prior to designation as a DLT. The following will be DLTs:

- Inability to reduce prednisone dose below 10 mg within 6 weeks (rather than 12 weeks) due to ongoing immune-related adverse reaction of Grade >1
- Any Grade 4 irAE not attributed to local tumor response (e.g., inflammatory reaction attributed to local tumor response or inflammatory reaction at sites of metastatic disease or lymph nodes)
- Any  $\geq$  Grade 3 colitis
- Any Grade encephalopathy
- Any  $\geq$  Grade 3 neurotoxicity
- Any  $\geq$  Grade 3 peripheral neuromotor syndromes
- Any Grade 2 or higher noninfectious pneumonitis irrespective of duration
- Any Grade 3 irAE, excluding colitis that does not downgrade to Grade 2 within 3 days after onset of the event despite optimal medical management including systemic corticosteroids or does not downgrade to  $\leq$  Grade 1 or baseline within 14 days

- Total bilirubin  $>1.5 - 3.0 \times$  ULN (Grade 2 Hyperbilirubinemia)
- ALT or AST  $>8 \times$  ULN
- ALT or AST  $>5 \times$  ULN for more than 2 weeks
- ALT or AST  $>3 \times$  ULN and
- ALT or AST  $>3 \times$  ULN and INR  $>1.5$
- ALT or AST  $>3 \times$  ULN with appearance of fatigue, nausea, vomiting, right upper quadrant pain or tenderness, fever, rash, and/or eosinophilia ( $>5\%$ )
- Any Grade  $\geq 3$  non-irAE toxicity that does not downgrade to Grade  $\leq 1$  or baseline status (for patients who entered the study with an existing laboratory abnormality) within 14 days
- Inability to receive  $\geq 75\%$  or more of scheduled study treatment (both Vicineum and durvalumab) during the first six weeks of the trial

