### 3.3.2 Vicineum

Following any biopsy or TURBT, study drug must be interrupted for a minimum of 1 week and maximum of 2 weeks before restarting Vicineum treatment. Patients who develop low grade papillary disease will be allowed to stay on trial. In November 2016, the FDA published a draft guidance for trials involving patients with BCG-unresponsive disease in which only high-risk disease counts as a recurrence or an event. In this clinical setting, low-risk disease would lead to transurethral resection while high-risk disease would lead to cystectomy, which is a much different clinical outcome. Therefore, in this trial, low grade recurrences will be documented but will not count as a trial-ending recurrence or event. Furthermore, low grade recurrences are considered to be downstaging of disease since the inclusion criteria requires patients with high grade disease.

Study drug administration must be postponed if a subject develops any Grade 3 or greater adverse event. Study treatment may resume when the AE returns to  $\leq$  Grade 1 or baseline or sooner if there is agreement between the investigator and the sponsor. Study treatment may be postponed at the discretion of the investigator for unrelated AEs, if this is considered in the best interest of the subject. If the causal relationship between Vicineum and an AE is initially uncertain, study drug should be interrupted until that determination is made. Also study treatment may be postponed for lower grade AEs at the investigator discretion if considered in the best interest of the subject.

The following specific criteria will be used for holding Vicineum dosing based on serum creatinine and calculation of creatinine clearance:

Baseline Creatinine	Criteria for Holding Vicineum Treatment*	
	Serum Creatinine	Creatinine Clearance
<1.0 mg/dl or <88 $\mu$ mol/L	>1.5 mg/dl or >133 $\mu$ mol/L	<40 ml/min or a decrease of 25% from baseline
$\geq$ 1.0 mg/dl or $\geq$ 88 $\mu$ mol/L	Increase to $>2 \times$ Baseline Value	<40 ml/min or a decrease of 25% from baseline

\*Vicineum dosing should be held if either the serum creatinine or the creatinine clearance criteria, as defined in this table, are met.

If changes in renal function are noted, the investigator should evaluate the subject for the etiology of these changes. Vicineum treatment may be resumed upon improvement or stabilization at creatinine of  $\leq 2 \times$  baseline or  $\leq 2 \times$  ULN.

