Assessments to be performed at the times stipulated in the table and as clinically required in the management of the subject  .	Screening	Baseline	All assessments to be performed pre-infusion unless stated otherwise						Post-Induction and Maintenance
			Week 1	Weeks 2 - 5	Week 6	Weeks 7 - 11	Week 12		
Day	-84 to -1	-7 to 0							
Week	-12 to -1	-1							
24 hour urine (only if CrCl to be measured rather than calculated)	X								
PPD testing (if indicated)	X								
Coagulation parameters	X		As clinically indicated						
Urine cytokines		X					X	6 months	
Serum circulating cytokine profile		X		Weeks 2, 3, and 5					

SCHEDULE OF STUDY ASSESSMENTS: Screening (Weeks -12 to -1), Induction Phase (Weeks 1 – 12), and Post-Induction Evaluation (All assessments can be performed within +/- 7 days of scheduled assessment to accommodate holidays and scheduling difficulties)									
Assessments to be performed at the times stipulated in the table and as clinically required in the management of the subject  .	Screening	Baseline	All assessments to be performed pre-infusion unless stated otherwise						Post-Induction and Maintenance
			Week 1	Weeks 2 - 5	Week 6	Weeks 7 - 11	Week 12		
Day	-84 to -1	-7 to 0							
Week	-12 to -1	-1							
sPD-L1 concentration (to assess target engagement)		X		Weeks 2, 3, and 5					
Gene expression analysis		X							
Tissue immune correlates (IHC and possibly RNAseq)		X						Last biopsy on trial	

**Abbreviated Title:** Durvalumab & Vicineum for NMIBC

**Version Date:** 05/22/2025

SCHEDULE OF STUDY ASSESSMENTS: Screening (Weeks -12 to -1), Induction Phase (Weeks 1 – 12), and Post-Induction Evaluation (All assessments can be performed within +/- 7 days of scheduled assessment to accommodate holidays and scheduling difficulties)								
Assessments to be performed at the times stipulated in the table and as clinically required in the management of the subject  .	Screening	Baseline	All assessments to be performed pre-infusion unless stated otherwise					
			Week 1	Weeks 2 - 5	Week 6	Weeks 7 - 11	Week 12	Post-Induction and Maintenance
Day	-84 to -1	-7 to 0						
Week	-12 to -1	-1						
Flow cytometry of PBMCs for immune subsets and antigen-specific responses (T-cell clonal expansion if feasible)		X					X	6 months
Immunogenicity assessment		X				Week 8: ADA	Week 12: AVA	

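### Entry accepts a 24-hour creatinine clearance but the Vicineum hold rule appears to use a calculated one, so the rules can conflict for a patient whose kidney function is unchanged

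*Combined protocol and SAP*

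**What the plan says.** **Entry.** Section 2.1.1.7 requires clearance above 40 mL/min by Cockcroft-Gault "or by 24-hour urine collection for determination of creatinine clearance". Either method is enough. Cockcroft-Gault is the only formula printed.

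**Screening and calendar.** Section 2.2 lists "24 hour urine (only if CrCL will not be calculated"; the Study Calendar (Section 3.4) has the row "24 hour urine (only if CrCl to be measured rather than calculated". The calendar marks that row at screening and nowhere else. Both entries set a measured clearance (24-hour urine) against a calculated one. Serum creatinine is part of the acute care panel, which is drawn at baseline (Section 2.4.1), weekly through induction and every two weeks afterwards.

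**Hold.** Section 3.3.2 states: "The following specific criteria will be used for holding Vicineum dosing based on serum creatinine and calculation of creatinine clearance". In both rows of its table the clearance criterion is "<40 ml/min or a decrease of 25% from baseline", and the footnote adds: "Vicineum dosing should be held if either the serum creatinine or the creatinine clearance criteria, as defined in this table, are met".

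**Resumption.** The same section lets Vicineum restart on improvement or stabilization at a serum creatinine no more than twice baseline or twice ULN. This test does not use clearance.

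**DLT.** Section 3.1.1 lists as a DLT the inability to receive at least 75% "of scheduled study treatment (both Vicineum and durvalumab) during the first six weeks of the trial".

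**The concern.** The 24-hour result decides eligibility only when the Cockcroft-Gault value is 40 mL/min or lower. If the hold test is then made on a calculated clearance, that patient is eligible and at the same time below the hold limit before any study drug is given.

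The relative criterion has a related weakness. The plan does not say which clearance value is the baseline. A patient who entered on a 24-hour collection may have only a measured value at screening, and later calculated values would be compared with it. A difference between methods could then be read as a fall in renal function.

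This is a Phase I safety trial. Section 3.3.2 says missed Vicineum doses are not made up, and shortfall in exposure during the first six weeks is one of the DLT items. A hold that reflects the choice of method rather than a change in the patient would lower exposure for no safety reason. Under some readings it could enter the 3+3 count.

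**Working it through.** No figure in the plan needs reproducing. The check applies the printed formula to the two rules.

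**1. The hold limit at baseline.** For men, Section 2.1.1.7 gives CrCl = weight × (140 − age) / (72 × creatinine); for women the result is multiplied by 0.85. The patients below are illustrative, and each is assumed to have a 24-hour value above 40.

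| Patient | Calculation | Calculated CrCl (mL/min) |
|---|---|---|
| Man, 75 y, 70 kg, 1.6 mg/dL | 70 × 65 / 115.2 | 39.5 |
| Man, 80 y, 60 kg, 1.3 mg/dL | 60 × 60 / 93.6 | 38.5 |
| Woman, 82 y, 55 kg, 1.1 mg/dL | 55 × 58 × 0.85 / 79.2 | 34.2 |
| Man, 75 y, 75 kg, 1.7 mg/dL | 75 × 65 / 122.4 | 39.8 |

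All four fail entry by formula, pass by 24-hour urine and are below the hold limit. The only exception is a calculated value of exactly 40, which fails entry by formula but does not trigger a hold. In an illustrative grid (40–120 kg, 50–95 years, creatinine 0.6–3.0 mg/dL, both sexes), 91 of 98,611 combinations at or below 40 equal exactly 40, or 0.09%.

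**2. The 25% criterion with mixed methods.** With a measured baseline M, a calculated value at or below 0.75 × M counts as a 25% fall. M is not given in the documents; a range of assumed values follows.

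| Measured baseline M | 0.75 × M |
|---|---|
| 45 | 33.75 |
| 50 | 37.5 |
| 55 | 41.25 |
| 60 | 45 |
| 70 | 52.5 |

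Above M = 40 / 0.75 = 53.3, the relative criterion can catch patients whose calculated value is over 40. The first patient's 39.5 becomes a 25% fall once M reaches 39.5 / 0.75 = 52.7, with no change in creatinine. At M = 50 it is a fall of 10.5 / 50 = 21%, and only the absolute limit applies.

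**3. The resumption wording for the same patient.** With creatinine unchanged at 1.6 mg/dL, the serum criterion for a hold (above 2 × 1.6 = 3.2) is not met. The clearance criterion (39.5, below 40) is met. The resumption figure (creatinine at or below 3.2) is also met. He satisfies the hold and resumption tests together.

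**4. The 75% item.** Weeks 1–6 schedule six Vicineum instillations and two durvalumab infusions (Weeks 2 and 6). Assume both infusions are given.

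| Instillations held | Vicineum alone | Both drugs pooled |
|---|---|---|
| 1 | 5/6 = 83% | 7/8 = 87.5% |
| 2 | 4/6 = 67% | 6/8 = 75%, passes |
| 3 | 3/6 = 50% | 5/8 = 62.5% |

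Two held instillations fall short only if the item is read per drug. A pooled shortfall needs three or more, and step 3 leaves it doubtful that a hold would last that long in a stable patient.

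**The case against.** The strongest reply is that Section 3.3.2 names no method. A clearance from a 24-hour collection also involves a calculation, and the table column says only creatinine clearance. The calendar allows assessments as clinically required, so the collection may be repeated for a patient who entered that way. This stands in part. The method is inferred from the contrast between measured and calculated in Sections 2.2 and 3.4, the single scheduled collection and the single printed formula. It is the most natural reading, but the text does not state it outright.

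Secondly, Section 2.2 presents the 24-hour collection as an alternative to the formula, not as a second chance after a failed formula result. That is fair. But a patient whose clearance was never calculated at screening can still turn out to be below 40 at the first on-study calculation.

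A reader might go further and infer three things that the documents do not support:

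- **That such a patient cannot be dosed.** The resumption wording is met at once if creatinine is stable, so the rules conflict and do not clearly bar dosing.
- **That held doses will be scored as DLTs.** At two held doses this needs the per-drug reading, and Section 3.1.1 sets aside toxicity clearly due to another etiology.
- **That false renal signals will appear in the safety tables.** Section 6.1 makes a laboratory value an adverse event only under listed conditions, and a held instillation with unchanged creatinine is not among them.

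**Conclusion.** The concern holds as a conflict between stated rules. On the most natural reading of Section 3.3.2, any patient who qualifies only by 24-hour urine and has a Cockcroft-Gault value below 40 meets the hold limit at baseline with unchanged kidney function. The 25% test can also mix methods. The same patient meets the resumption wording, so the plan gives no clear answer on dosing.

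This assumes that the hold test uses the printed formula and that the calculated value does not change materially between screening, which may be up to 12 weeks earlier, and the first dose. It does not extend to patients who had a 24-hour collection but whose calculated value is also above 40, except through the 25% test.

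Loss of exposure is possible. A DLT from two held instillations is possible only if the 75% item is read per drug and the hold is not set aside as having another cause. The documents do not show how many patients enter by the 24-hour route or how far the methods differ, so the number affected is unknown and could be nil. The correction is worth making because it is cheap and removes a conflict from a dosing rule.

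**What to change.** Reconcile Sections 2.1.1.7, 2.2, 3.3.2 and 3.4 so that they state which clearance method governs entry, which value is the baseline, and which method the hold test uses. The text should say explicitly how the below-40 and 25% criteria, and the resumption wording, apply to a patient admitted by 24-hour urine.

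Record calculated clearance at baseline for every patient, including those admitted by 24-hour urine, so that change from baseline can be compared within one method. The creatinine and weight needed are already collected at baseline, so this adds no test.

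No threshold or clinical rule is proposed here; those choices belong to the sponsor. The cost is a short protocol clarification. The small downside is that, depending on how the sections are reconciled, a few borderline patients may change eligibility.

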2.1.1.12 Body weight > 30 kg

## **2.1.2 Exclusion Criteria**

2.1.2.1 Patients who are receiving any other investigational agents.

2.1.2.2 QT interval corrected for heart rate using Fridericia's formula (QTcF) ≥470 ms. [Any clinically significant abnormalities detected require triplicate ECG results and a mean

QT interval corrected for heart rate using Fridericia's formula (QTcF)  $\geq$ 470 ms calculated from 3 ECGs.]

- 2.1.2.3 History of allergic reactions attributed to compounds of similar chemical or biologic composition to Vicineum or durvalumab or other agents used in the study.
- 2.1.2.4 Uncontrolled intercurrent illness including, but not limited to, ongoing or active infection, symptomatic congestive heart failure, unstable angina pectoris, cardiac arrhythmia, or psychiatric illness/social situations that would limit compliance with study requirements. Urinary tract infections (UTIs) are excluded from being an exclusion criterion for treatment unless they are grade 3 or higher.
- 2.1.2.5 Pregnant women are excluded from this study because it is unknown whether Vicineum and/or durvalumab have any teratogenic effects. In nursing mothers, breastfeeding should be discontinued as these medications may have the potential risk for adverse events in nursing infants secondary to treatment of the mother.
- 2.1.2.6 Any previous treatment with a PD1 or PD-L1 inhibitor, including durvalumab
- 2.1.2.7 Evidence of non-bladder urothelial (transitional cell) carcinoma by biopsy, cytology, or radiological imaging within the past 2 years of treatment (e.g. upper tract transitional cell carcinoma, urethral urothelial carcinoma).
- 2.1.2.8 Subjects with hydronephrosis, except for those subjects where hydronephrosis has been longstanding (i.e., predates the diagnosis of the CIS, Ta, or T1 by more than 2 years) and diagnostic evaluation at screening shows no evidence of tumor causing the hydronephrosis.
- 2.1.2.9 Any other anticancer therapy (e.g., chemotherapy, biologic therapy, immunotherapy, targeted therapy, endocrine therapy, radiation therapy, intravesical therapy, investigational agent) within 28 days of the first dose of study therapy (and within 6 weeks for nitrosourea or mitomycin C) other than a single dose of intravesical chemotherapy which is permitted between 28 days and 14 days prior to the first dose of study treatment.
- 2.1.2.10 The subject has a diagnosis of another malignancy within 2 years before the first dose of study treatment, except for superficial skin cancer, localized prostate cancer on active surveillance, or localized solid tumors deemed cured by surgery and not treated with systemic anticancer therapy and not expected to require anticancer therapy in the next 2 years i.e., while the subject may be taking study treatment.
- 2.1.2.11 Current or prior use of immunosuppressive medication within 28 days before the first dose of durvalumab, with the exceptions of intranasal and inhaled corticosteroids or systemic corticosteroids at physiological doses, which are not to exceed 10 mg/day of prednisone, or an equivalent corticosteroid.
- 2.1.2.12 Active or prior documented autoimmune or inflammatory disorders (including inflammatory bowel disease [e.g. colitis or Crohn's disease], diverticulitis [with the exception of diverticulosis], systemic lupus erythematosus, Sarcoidosis syndrome, or Wegener syndrome [granulomatosis with polyangiitis, Graves' disease, rheumatoid arthritis, hypophysitis, uveitis, etc.]). The following are exceptions to this criterion:

- Subjects with vitiligo or alopecia
- Subjects with hypothyroidism (e.g. following Hashimoto syndrome) stable on hormonal replacement
- Any chronic skin condition that does not require systemic therapy
- Subjects without active disease in the last 5 years may be included but only after consultation with the Principal Investigator
- Subjects with celiac disease controlled by diet alone

2.1.2.13 History of primary immunodeficiency.

2.1.2.14 History of allogeneic organ transplant.

2.1.2.15 History of hypersensitivity to durvalumab or any excipient

2.1.2.16 History of hypersensitivity to Vicineum or its components

2.1.2.17 Active infection with tuberculosis (clinical evaluation that includes clinical history, physical examination, and radiographic findings, and PPD testing if indicated), hepatitis B (known positive HBV surface antigen (HBsAg) result, hepatitis C, or human immunodeficiency virus (positive HIV 1/2 antibodies). Patients with HIV are excluded from participating on this clinical trial because their immunodeficiency would confound the evaluation of adverse events which would hinder meeting the primary objective. Subjects with a past or resolved HBV infection (defined as the presence of hepatitis B core antibody [anti-HBc] and absence of HBsAg) are eligible. Subjects positive for hepatitis C (HCV) antibody are eligible only if polymerase chain reaction is negative for HCV RNA.

